ANNEX 3. REFERENCE SAFETY INFORMATION

Please refer to the SmPC:

https://www.ema.europa.eu/en/documents/product-information/jyseleca-epar-product-information_en.pdf

ANNEX 4. DEFINITION OF BASELINE DISEASES IN ARTIS, BIOBADASER, BSRBR-RA, DANBIO, AND RABBIT

The following medical code-lists were created for the long-term safety PASS (GS-EU-417-9047) and were reviewed by the registries.

	BSRBR-RA, RABBIT, BIOBADASER	ARTIS, DANBIO
Safety Risk	Operationalization (final list to be defined based on reported endpoints in each register)	Operationalization
Serious and opportunistic infections	Hospitalization and/or use of parenteral antibiotics + MedDRA Infections and Infestations SOC 10021881.	Hospitalizations in the Patient Register listing as main diagnosis ICD10codes below. If main diagnosis is RA, contributory diagnoses are also considered. A00B99 (excluding A33 and A50), D73.3, E32.1, G00G02, G04.2, G05G07, H00.0, H44.0, H60.0H60.3, H66H67, H70, I30.1, I40.0, J00J22, J32, J34.0, J36, J39.0J39.1, J44.0, J85, J86, K04.4, K04.6, K04.7, K10.2, K11.3, K12.2, K14.0, K57.0, K57.2, K57.4, K57.8, K61, K63.0, K65.0, K65.1, K65.2, K65.9, L00L08, L30.3, M00M01, M46.2M46.5, M60.0, M65.0, M71.0, M71.1, M72.6, M86, N13.6, N15.1, N15.9, N30.0, N30.8, N34.0, N41.2, N43.1, N45.2, N45.3, N45.4, N48.2, N61, N70, N73, N75.1.
Herpes zoster/ Varicella zoster	10019974 Herpes zoster, 10019983 Herpes zoster ophthalmic, 10030865 Ophthalmic herpes zoster, 10058428 Herpes zoster multidermatomal, 10063491 Herpes zoster oticus, 10065038 Herpes zoster disseminated, 10065119 Necrotising herpetic retinopathy, 10072210 Genital herpes zoster, 10074241 Varicella zoster gastritis, 10074245 Herpes zoster pharyngitis, 10074248 Herpes zoster meningoencephalitis, 10074253 Herpes zoster necrotising retinopathy, 10074254 Varicella zoster pneumonia, 10074254 Varicella zoster pneumonia, 10074259 Herpes zoster meningitis, 10074297 Herpes zoster cutaneous disseminated.	Hospitalizations in the Patient Register listing as main diagnosis ICD10codes A02, A15A19, A31, A32, A43, A48.1, B02, B38, B39, B40, B44, B45, B58, B59. If main diagnosis is RA, contributory diagnoses are also considered.
Malignancy	Malignant or unspecified tumours.	All invasive malignancies recorded in the cancer register, excluding NMSC.

Nonmelanoma skin cancer (NMSC)	10004146 Basal cell carcinoma; 10004178 Basosquamous carcinoma; 10004179 Basosquamous carcinoma of skin; 10006059 Bowen's disease; 10007390 Carcinoma in situ of skin; 10064055 Lip squamous cell carcinoma; 10063693 Malignant neoplasm of eyelid; 10040808 Skin cancer; 10055115 Skin cancer metastatic 10041834 Squamous cell carcinoma of skin.	Identified through the Cancer register as all malignancies with ICDO/2 code C44 and D04, plus ICD7 code 191, and all basal cell cancers recoded in the register's subcomponent on basal cell cancers.
Gastrointestinal (GI) perforation	10000099 Abdominal wall abscess; 10000285 Abscess intestinal; 10000582 Acquired tracheoesophageal fistula; 10002156 Anal fistula; 10002157 Anal fistula excision; 10002248 Anastomotic ulcer perforation; 10002924 Aortoduodenal fistula; 10003012 Appendicitis perforated; 10009995 Colonic fistula; 10013536 Diverticular fistula; 10013538 Diverticulitis; 10013541 Diverticulitis intestinal haemorrhagic; 10013828 Duodenal fistula; 10013832 Duodenal perforation; 10013849 Duodenal ulcer perforation; 10013849 Duodenal ulcer perforation; 10013850 Duodenal ulcer perforation, nonobstructive; 10017815 Gastric perforation; 10017835 Gastric ulcer perforation; 10017836 Gastric ulcer perforation, obstructive; 10017866 Gastritis haemorrhagic; 10017877 Gastrointestinal fistula; 10017954 Gastrointestinal gangrene; 10017955 Gastrointestinal haemorrhage; 10018001 Gastrointestinal perforation; 10021305 Ileal perforation; 10021310 Ileal ulcer perforation; 10022647 Intestinal fistula; 10022694 Intestinal perforation; 10023174 Jejunal perforation; 10023178 Jejunal ulcer perforation; 10023804 Large intestine perforation; 10030181 Oesophageal perforation; 10034354 Peptic ulcer perforation; 10034358 Peptic ulcer perforation, obstructive; 10034397 Perforated peptic ulcer oversewing; 10034649 Peritoneal abscess; 10034674 Peritonitis; 10038073 Rectal perforation; 10038975 Retroperitoneal abscess; 10041103 Small intestinal perforation; 10046274 Upper gastrointestinal haemorrhage; 10048946 Anal abscess; 10048947 Rectal abscess; 10049583 Douglas' abscess; 10049764 Appendiceal abscess; 10050362 Anovulvar fistula; 10050953 Lower gastrointestinal haemorrhage; 10051425 Enterocutaneous fistula; 10052211 Oesophageal rupture; 10052457 Perineal abscess; 10052488 Oesophageal ulcer perforation; 10052814 Perirectal abscess; 10052931 Colon fistula repair; 10052991 Intestinal fistula repair; 10053267 Rectal fistula repair; 10056086 Paraoesophageal abscess; 10056346 Anastomotic haemorrhage; 10056991 Enterocolonic fistula; 10056992 Oesophagobronchial fistula; 10058381 Oesophageal fistula repair; 10059175 Intestinal haemorrhage; 10060921 Abdominal abscess; 10061248 Intestinal ulcer perforation; 10061249 Intraabdominal haemorrhage; 10061820 Diverticular perforation; 10061975 Gastrointestinal ulcer	Main diagnosis recorded in the inpatient component of the Patient Register listing ICD10codes: K22.3, K25.1, K25.2, K25.5, K25.6, K26.1, K26.2, K26.5, K26.6, K27.1, K27.2, K27.5, K27.6, K28.1, K28.2, K28.5, K28.6, K31.6, K35.0, K35.1, K57.0, K57.2, K57.4, K57.8, K63.0, K63.1, K63.2. If main diagnosis is RA (ICD10 codes M05, M06.0, M06.2, M06.3, M06.8, M06.9, M12.3), contributory diagnoses are also allowed.

	
perforation; 10062065 Perforated ulcer; 10062070 Peritonitis bacterial; 10062570 Enterovesical fistula; 10065713 Gastric fistula; 10065879 Gastrointestinal anastomotic leak; 10066870 Aortooesophageal fistula; 10066892 Rectourethral fistula; 10067091 Gastropleural fistula; 10068792 Gastrosplenic fistula; 10071647 Infectious peritonitis.
	

MACE
	
Fatal and nonfatal : 10000891 Acute myocardial infarction; 10006147 Brain stem infarction; 10006148 Brain stem ischaemia; 10008034 Cerebellar infarction; 10008088 Cerebral artery embolism; 10008120 Cerebral ischaemia; 10008190 Cerebrovascular accident; 10014498 Embolic stroke; 10019005 Haemorrhagic cerebral infarction; 10019016 Haemorrhagic stroke; 10024033 Lateral medullary syndrome; 10028596 Myocardial infarction; 10028602 Myocardial necrosis; 10033697 Papillary muscle infarction; 10043647 Thrombotic stroke; 10049768 Silent myocardial infarction; 10051078 Lacunar infarction; 10055677 Haemorrhagic transformation stroke; 10056237 Migrainous infarction; 10059613 Stroke in evolution; 10060839 Embolic cerebral infarction; 10060840 Ischaemic cerebral infarction; 10061256 Ischaemic stroke; 10062573 Brain stem thrombosis; 10064961 Thalamic infarction; 10066591 Post procedural stroke; 10066592 Post procedural myocardial infarction; 10067167 Cerebellar embolism; 10067347 Thrombotic cerebral infarction; 10067462 MillardGubler syndrome; 10068621 Cerebellar ischaemia; 10068644 Brain stem stroke; 10069020 Basal ganglia infarction; 10070671 Cerebral septic infarct; 10070754 Inner ear infarction; 10071043 Basal ganglia stroke; 10071260 Carotid angioplasty; 10073945 Perinatal stroke; 10074422 Brain stem embolism.
 
Fatal only: 10002886 Aortic aneurysm rupture; 10003173 Arterial rupture; 10003210 Arteriosclerosis; 10003212 Arteriosclerosis moenckebergtype; 10006145 Brain stem haemorrhage; 10007522 Cardiac asthma; 10007554 Cardiac failure; 10007556 Cardiac failure acute; 10007558 Cardiac failure chronic; 10007559 Cardiac failure congestive; 10007559 Cardiac failure congestive; 10007560 Cardiac failure high output; 10007625 Cardiogenic shock; 10007684 Carotid arterial embolus; 10007686 Carotid artery aneurysm; 10007688 Carotid artery thrombosis; 10008023 Cerebellar artery thrombosis; 10008030 Cerebellar haemorrhage; 10008076 Cerebral aneurysm ruptured syphilitic; 10008086 Cerebral arteriovenous malformation haemorrhagic; 10008089 Cerebral artery occlusion; 10008092 Cerebral artery thrombosis; 10008111 Cerebral haemorrhage; 10008118 Cerebral infarction; 10008132 Cerebral thrombosis; 10018985 Haemorrhage intracranial; 10022758 Intracranial aneurysm; 10022840
	
Combines MI, stroke, and fatal cardiovascular events: I00I99 as main cause of death, or I20.0, I21, I60I64 as diagnosis in in or outpatient care.

	
Intraventricular haemorrhage; 10022841 Intraventricular haemorrhage neonatal; 10024119 Left ventricular failure; 10024242 Leriche syndrome; 10034476 Pericardial haemorrhage; 10036511 Precerebral artery occlusion; 10039163 Right ventricular failure; 10039330 Ruptured cerebral aneurysm; 10042316 Subarachnoid haemorrhage; 10042434 Sudden death; 10047279 Ventricle rupture; 10048380 Aneurysm ruptured; 10048761 Atrial rupture; 10049418 Sudden cardiac death; 10049993 Cardiac death; 10050403 Carotid artery dissection; 10051093 Cardiopulmonary failure; 10051328 Carotid aneurysm rupture; 10052019 Femoral artery occlusion; 10053633 Cerebellar artery occlusion; 10053649 Vascular rupture; 10053949 Vascular pseudoaneurysm ruptured; 10055803 Haemorrhage coronary artery; 10058178 Aortic occlusion; 10060874 Aortic rupture; 10060953 Ventricular failure; 10060964 Arterial haemorrhage; 10062585 Peripheral arterial occlusive disease; 10062599 Arterial occlusive disease; 10063081 Acute left ventricular failure; 10063082 Acute right ventricular failure ; 10063083 Chronic left ventricular failure; 10063084 Chronic right ventricular failure; 10064595 Haemorrhagic arteriovenous malformation; 10064601 Iliac artery occlusion; 10065441 Venous haemorrhage; 10065558 Aortic arteriosclerosis; 10067057 Basal ganglia haemorrhage; 10067116 Carotid arteriosclerosis; 10068119 Aortic dissection rupture; 10068119 Aortic dissection rupture; 10068230 Cardiorenal syndrome; 10069694 Brachiocephalic artery occlusion; 10069695 Subclavian artery occlusion; 10069696 Coeliac artery occlusion; 10071716 Vertebral artery dissection; 10072043 Central nervous system haemorrhage; 10072789 Iliac artery rupture; 10073565 Intracranial artery dissection; 10073565 Intracranial artery dissection; 10073681 Epidural haemorrhage; 10075449 Brachiocephalic arteriosclerosis; 10076203 Radiation associated cardiac failure.
	

Venous thromboembolism (deep venous thrombosis and pulmonary embolism)
	
10037377 Pulmonary embolism; 10051055 Deep vein thrombosis; 10061408 Venous thrombosis limb; 10063909 Post procedural pulmonary embolism; 10066881 Deep vein thrombosis postoperative.
	
Main diagnosis in the Patient Register, in or outpatient component, of the following ICD10 codes: I26.9, I26.0, I80.1, I80.2, I80.3, I80.8, I80.9, I81.0, I82.0, I82.1, I82.2, I82.3, I82.8, I82.9. Or, pulmonary embolism I26.0 listed as the underlying cause of death.


Hyperlipidemia
	
BIOBADASER: Lipid measures LDL, HDL, total cholesterol or triglycerides may be captured according to clinical practice.
	
Patients who will initiate treatment with statins and other lipid-lowering drugs.

	
BSRBR-RA: Patients who will initiate treatment with statins or other lipid-lowering drugs.
 
RABBIT: Hyperlipidemia reported as adverse event by the treating physician.
	
--	--	--

Other medical history

Disease	Data source	ICD10
Malignancy	The Cancer register	All except benign tumors
Infection	Main diagnoses from the Inpatient component of Patient Register.	A00B99, D73.3, E06.0, E32.1, G00G02, G04.2, G05G07, H00.0, H44.0, H60.0H60.3, H66H67, H70, I30.1, I40.0, J00J22, J32, J34.0, J36, J38.3, J39.0J39.1, J44.0, J85, J86, K04.4, K04.6, K04.7, K10.2, K11.3, K12.2, K14.0, K57.0, K57.2, K57.4, K57.8, K61, K63.0, K65.0, K65.1, K65.2, K65.9, L00L08, L30.3, M00M01, M46.2M46.5, M60.0, M65.0, M71.0, M71.1, M72.6, M86, N10, N11, N12, N13.6, N15.1, N15.9, N30.0 N30.8, N34.0, N41.2, N43.1, N45.2, N45.3, N45.4, N48.2, N61, N70, N73, N75.1
Renal impairment		N18, N18.1, N18.2, N18.3, N18.4, N18.5
Knee or hip prosthesis	Operation codes from the Patient register	NGB, NFB
Diabetes	The Patient Register	E10E14, O24
Myocardial infarction	The Patient Register	I21, I22

SIGNATURE PAGE – INVESTIGATOR

Study Title: Non-interventional post-authorization cohort safety study evaluating the effectiveness of the additional risk minimization measures for filgotinib (Jyseleca®) use in patients with moderate to severe active rheumatoid arthritis within European registries

CSP Version:

1.0

Date:

02-Feb-2022

I, the undersigned, have read this non-interventional study protocol and will conduct the study as described in compliance with the study protocol, in accordance with the guidelines of Good Pharmacoepidemiology Practises and Heads of Medicines Agencies Good Pharmacovigilance Practices.

Investigator Name

Signature

Date

SIGNATURE PAGE – SPONSOR

Study Title: Non-interventional post-authorization cohort safety study evaluating the effectiveness of the additional risk minimization measures for filgotinib (Jyseleca®) use in patients with moderate to severe active rheumatoid arthritis within European registries

CSP Version: 1.0 **Date:** 02-Feb-2022

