The risk management plan (RMP) classifies MACE and VTE as “*important potential risks*,” while serious and opportunistic infections (and herpes zoster) are considered “*important identified risks*.” TB and other opportunistic infections are more frequent in patients with RA; the reasons are likely multifactorial although increased risk has been identified with the use of glucocorticoids and other biologic DMARDs. To date there have been no safety signals arising from the filgotinib clinical development program for MACE, however the potential role of hyperlipidemia on the risk of MACE warrants continued assessment. Regarding VTEs, there was no imbalance in the occurrence of these events from the clinical development program however the RMP states “*With RA patients and patients with ulcerative colitis having a higher risk of VTEs, and VTEs having been associated with some JAK inhibitors, venous thromboembolism (DVT/PE) has been classified as an important potential risk*”.

Pregnancy is a contraindication for filgotinib as teratogenicity was observed in animals. Thus, women of childbearing potential must be encouraged to use effective contraception during treatment and for at least 1 week after stopping filgotinib treatment.

Serious and opportunistic infections (including herpes zoster and TB) are higher in patients with RA and is increased with the use of prednisone and some biological DMARDs. Thus, there may be increased risk of such infections among patients with poor immune systems or due to the use of immunosuppressant medication.

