8.3. Variables

8.3.1. Baseline Variables

Baseline variables are collected at index date. These variables reflect the patient's demographics and status at the initiation of filgotinib treatment including relevant medical history at or prior to the index date. Age (or date of birth), sex, disease duration and DAS28 are recorded at baseline for all registries.

Risk factors for MACE, VTE, and Serious and Opportunistic Infections

Variables will be collected at baseline to define the risk of each of the 3 outcomes of concern: MACE, VTE, and serious and opportunistic infections (see definitions in Section 6.1 and Annex 4).

The set of risk factor definitions were derived utilizing broader representation than that solely included in the RMP and then checked against data availability in each registry. The set of risk factors are provided in tables in each of the registry-specific sections, which reflect the availability of variables for each registry.

For MACE, the UK's Q-Risk score was used as a guide (Hippisley-Cox et al., 2008). We note that RA is a risk factor for MACE/CVD implying that the indicated patient population are at higher risk than the general population (after adjusting for age and sex). RA is available in all registries as a risk factor, as all patients have RA.

For VTE, the Jyseleca RMP mentions the following risk factors for VTE: "*prior history of VTE, advanced age, hormone replacement treatment, obesity, smoking, cancer or immobilization*". These risk factors are supplemented by considering the Caprini Score (Bahl et al., 2010), a perioperative assessment tool for new VTE. The Caprini Score highlighted the importance of a lack of mobility and hospitalization have on VTE risk.

For serious and opportunistic infections, the RMP highlighted that patients with RA were at increased risk and that the "*The reasons are multifactorial, including a poorly functioning immune system and concomitant use of immunosuppressant medications such as glucocorticoids*". The use of immunomodulators implies that patients initiating filgotinib are already at increased levels of risk. The set of risk factors for infection were supplemented by those indicated by the Rheumatoid Arthritis Observation of Biologic Therapy (RABBIT) Risk Score for serious infections (Zink et al., 2014).

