In accordance with the RMP, SmPC and the description provided in Section 6.2, the following variables will be used to describe the adherence of the prescribing physician with respect to the Guide for HCP:

- Diagnosis of TB: yes/no
 - Date of diagnosis
- Diagnosis of herpes zoster: yes/no
 - Date of diagnosis
- Diagnosis of viral hepatitis: yes/no
 - Date of diagnosis
- Patient is currently pregnant (defined as greater than 25 weeks): yes/no
- Date of most recent full term pregnancy (for women aged <50 years old)
- Recent diagnosis of serious and opportunistic infection: yes/no
 - Type of infection
 - Date of diagnosis

Dose and age are already variables for this study and thus the use of 100 mg in patients aged ≥ 75 years old and in patients with chronic kidney disease can be addressed.

Concomitant Medication

The SmPC includes a warning that certain concomitant treatments should be avoided. Specifically, combination of filgotinib with other potent immunosuppressants such as azathioprine, ciclosporin, tacrolimus, biologic DMARDs, or other JAK inhibitors is not

recommended as a risk of additive immunosuppression cannot be excluded. For this reason, concomitant use will be recorded; this will not include any previous medication that is discontinued once filgotinib is first prescribed. Thus, this will capture those immunosuppressants that are prescribed to start with filgotinib or that are ongoing.

- Concomitant use of other immunosuppressant:
 - Type, name, and dose (incomplete)
 - Dates of dispensing

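### Annex 4 defines herpes zoster in ARTIS and DANBIO by 14 ICD-10 entries of which only B02 is zoster, so the baseline zoster variable there would count other infections

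*Protocol*

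**What the plan says.** Annex 4 of the protocol is titled as the definition of baseline diseases in all five registries. It has two code columns, MedDRA terms for BSRBR-RA, RABBIT and BIOBADASER and ICD-10 codes for ARTIS and DANBIO. It states that the lists were created for the long-term safety study GS-EU-417-9047 and reviewed by the registries.

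In the herpes zoster/varicella zoster row, the MedDRA cell begins "10019974 Herpes zoster, 10019983 Herpes zoster ophthalmic, 10030865 Ophthalmic herpes zoster, 10058428 Herpes zoster multidermatomal" and continues in the same vein. The ARTIS/DANBIO cell reads "Hospitalizations in the Patient Register listing as main diagnosis ICD10codes A02, A15A19, A31, A32, A43, A48.1, B02, B38, B39, B40, B44, B45, B58, B59", and also admits contributory diagnoses when the main diagnosis is RA.

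The row above, for serious and opportunistic infections, has its own ARTIS/DANBIO list, which opens "A00B99 (excluding A33 and A50), D73.3, E32.1".

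The physician-adherence lists for ARTIS (Section 8.3.1.1) and DANBIO (Section 8.3.1.4) each contain "Diagnosis of herpes zoster: yes/no", with a date, as an item separate from the diagnosis of TB. Section 6.1 also names zoster apart from the wider infection category: "while serious and opportunistic infections (and herpes zoster) are considered" important identified risks.

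**The concern.** The two cells of one row should describe the same condition, and they do not. One is a list of zoster terms. The other is a list of assorted infections that happens to include zoster. A programmer in Sweden or Denmark who follows the cell would flag as herpes zoster a patient hospitalised with tuberculosis, listeriosis or a fungal infection.

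At stake is one baseline adherence variable in two of the five registries. Zoster is a topic of the healthcare professional guide that the study evaluates, so its proportion will be read in the consolidated report to EMA and MHRA. From ARTIS and DANBIO that proportion would carry the wrong label, and it could not be set beside the figures from the other three registries.

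**Working it through.** No sample size, power or precision figure is involved, and the plan states no number on this point to reproduce. The check is a count and a comparison of cells. ICD-10 meanings are taken from the standard classification, because the protocol does not print them. The extracted text shows A15A19 without its hyphen; it is read as the range A15-A19, like A00B99 in the row above.

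**Count of the ARTIS/DANBIO zoster cell**

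- Entries: A02, A15-A19, A31, A32, A43, A48.1, B02, B38, B39, B40, B44, B45, B58, B59 = 14.
- With A15-A19 expanded to five codes: 14 - 1 + 5 = 18 codes.
- Zoster: B02 only, so 1 of 14 entries (1 of 18 codes).
- Not zoster: 14 - 1 = 13 entries (18 - 1 = 17 codes). These are salmonella (A02), tuberculosis (A15-A19), other mycobacteria (A31), listeriosis (A32), nocardiosis (A43), legionellosis (A48.1), mycoses (B38, B39, B40, B44, B45), toxoplasmosis (B58) and pneumocystosis (B59).

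**Count of the MedDRA zoster cell**

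- 16 entries, one of them (varicella zoster pneumonia) printed twice, so 15 distinct terms.
- All are herpetic, and all but necrotising herpetic retinopathy name zoster. None is a tuberculosis, listeria, legionella or fungal term.

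**Comparison with the row above.** The serious and opportunistic infection list for ARTIS/DANBIO covers A00-B99 except A33 and A50. Neither exclusion appears among the 14 entries, so every code in the zoster cell is already in that row, under the same rule of hospitalisation with main diagnosis (or contributory if RA is main). Taking the 13 non-zoster entries out of the zoster row loses no infection from Annex 4.

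**Is the cell provisional?** The caveat "Operationalization (final list to be defined based on reported endpoints in each register" heads only the MedDRA column. The ARTIS/DANBIO column carries no such caveat, and no other zoster list for these two registries appears in the protocol.

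**Effect on the variable.** Among n patients, let z be those with a qualifying B02 hospitalisation and o those with none but with a qualifying hospitalisation for one of the other entries. The cell as written reports (z + o)/n. A B02-only list reports z/n. The excess is o/n, and the share of flagged patients who truly meet the zoster code is z/(z + o). The protocol gives no value for z or o. The ratio 13 of 14 counts codes and says nothing about this share.

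**The case against.** The strongest reply concerns reach. Herpes zoster is not among the Section 7 objectives, is not a follow-up endpoint in Table 9, is not named in Section 8.7 and is not one of the stated contraindications. B02 is on the list, so hospitalised zoster is still found and the fault is over-inclusion. All of this stands and limits the point to one descriptive variable.

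The link from the adherence item to Annex 4 is also inferred. The body cites the Annex ("see definitions in Section 6.1 and Annex 4") for MACE, VTE and serious and opportunistic infections, and the zoster item carries no reference. That stands in part. But the Annex title covers baseline diseases in all five registries, and it holds the only zoster code list in the protocol. A row shifted in the PDF conversion cannot be wholly excluded either. Against that, the cell is a complete rule and the row above has its own full list.

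Four stronger readings are tempting, and the documents do not support them:

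- **That the TB objective is damaged because Annex 4 has no TB row.** TB is a separate variable, and nothing says it will be derived from the zoster cell. Viral hepatitis and pregnancy have no row either. A TB code list may be left to the statistical analysis plan.
- **That the absence of B01 (varicella) is an error.** The MedDRA cell has no plain varicella term, only varicella zoster gastritis and pneumonia, so the columns do not clearly disagree on this.
- **That outpatient zoster is missed in two registries and captured in three.** The MedDRA cell states no hospitalisation condition, but that does not show full capture of mild zoster. For BSRBR-RA, Section 8.4.3 describes MedDRA coding of serious morbidities.
- **That outpatient or any-position diagnoses must be added.** Hospitalisation with main diagnosis is also the ARTIS/DANBIO rule for serious infections, and an inpatient main diagnosis is the rule for gastrointestinal perforation. Widening it is a choice of case definition. According to Section 8.4, the Swedish register covers only non-primary outpatient care and the Danish one hospital contacts, so zoster seen only in primary care would still be missed.

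**Conclusion.** The cell is wrong as written. This is a wrong definition, so it is not a detail left open for the statistical analysis plan. Thirteen of its 14 entries are not zoster, and it contradicts the other cell of its own row. If it is applied, baseline herpes zoster in ARTIS and DANBIO will include hospitalised non-zoster infections, will double-count a hospitalised TB case under TB and zoster, and will not be comparable with the other three registries.

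The consequence is confined to this descriptive variable in two registries. No Section 7 objective is shown to be affected. The number of misclassified patients is unknown.

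The conclusion rests on three assumptions: standard ICD-10 meanings, the row alignment shown in the text, and use of Annex 4 to derive the adherence item. That the misplaced list was meant for opportunistic infections is a reasonable inference from its content, but the protocol does not say so.

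**What to change.** - Replace the ARTIS/DANBIO list in the zoster row with a zoster-specific code (B02).
- Move the existing list to a row of its own with its proper label, apparently opportunistic infections. Alternatively delete it, since A00-B99 in the row above already contains every code.
- State in the row that hospitalisation with main diagnosis (or contributory if RA is main) applies to ARTIS and DANBIO and is not stated in the MedDRA zoster cell, so that readers do not assume full comparability after the code change. Whether to add outpatient or any-position diagnoses is for the sponsor to decide and is not part of this error.
- Check GS-EU-417-9047, for which the lists were created, for the same cell.

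The cost is an annex correction and one changed code list in two registries, with a re-run if that variable has already been derived. No data collection changes, and no infection drops out of the Annex.

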8.3.2. Variables to be Collected During Patient Follow-up

The variables to be collected during the follow-up which will describe endpoints (see Section 6.2) related to aRMMs adherence are provided in the following table. These therefore include pregnancy, use of vaccines and lipid monitoring. Monitoring of TB following the initial screening for latent disease is not included: firstly, testing is not required and; secondly, evaluating whether clinicians routinely check for signs and symptoms is not be feasible via registry data.

As well as the occurrence of the variables, appropriate dates will be collected. Furthermore, the patients' index dates, end of treatment and end of follow-up dates will be used to estimate the exposure time.

Table 9 Availability of Endpoints to Assess Adherence by Registry During Patient Follow-up

Follow-up Variable	ARTIS	BIOBADASER	BSRBR-RA	DANBIO	RABBIT
Pregnancy	Yes	Yes	Yes	Yes	Yes
Dx of incident TB	Yes	Yes	Yes	Yes	Yes
Viral hepatitis	Yes	Yes	Yes	Yes (only history)	Yes
Administration of live attenuated vaccine	No	Yes	Yes (HZ only)	No	Yes
Lipid monitoring (approx.. 12 weeks after initiation of filgotinib)	No	Yes	No	No	No

Dx = diagnosis, HZ = herpes zoster, TB = tuberculosis

In addition to the above variables, the occurrence of a VTE event whilst the patient is using filgotinib will be identified and specifically the subsequent treatment pattern occurring such as discontinuation of filgotinib will be recorded.

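### Annex 4 requires a main diagnosis for VTE in ARTIS and DANBIO, without the RA exception used in other rows, so a past VTE coded only as contributory is missed from VTE history

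*Protocol*

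**What the plan says.** **VTE row.** In the ARTIS/DANBIO column of Annex 4, a VTE is a "Main diagnosis in the Patient Register, in or outpatient component, of the following ICD10 codes: I26.9, I26.0" and further listed codes. The only other route is "pulmonary embolism I26.0 listed as the underlying cause of death". The row does not say what happens when RA holds the main position.

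**Other rows of that column.** Serious infections start from "Hospitalizations in the Patient Register listing as main diagnosis ICD10codes below" and continue with "If main diagnosis is RA, contributory diagnoses are also considered". The herpes zoster row carries the same sentence. The gastrointestinal perforation row, limited to inpatient care, says that with RA as main diagnosis "contributory diagnoses are also allowed". Non-fatal MACE is "I20.0, I21, I60I64 as diagnosis in in or outpatient care", with no mention of position.

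**Where the definition is used.** Section 8.3.1 refers to Section 6.1 and Annex 4 for the definitions behind the baseline risk variables. History of VTE is a VTE risk factor in Table 3 (ARTIS) and Table 7 (DANBIO). Section 7 has an objective on filgotinib discontinuation after a VTE. For that objective Section 8.3.2 says only that "the occurrence of a VTE event whilst the patient is using filgotinib will be identified" and names no code list.

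**The concern.** The authors of Annex 4 knew that in an RA cohort the main diagnosis may be RA itself and push another condition into a contributory position. They provided for this in three rows, set no position limit in others, and left VTE strict without giving a reason.

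The strict rule fits past VTE least well. Annex 4 states that its lists were made for the long-term safety study. A main-diagnosis filter can suit an incident event there, but an old VTE may survive in the register only as a secondary code. Prior VTE is also the first VTE risk factor in the RMP text quoted in Section 8.3.1. At stake is the proportion of starters in Sweden and Denmark shown as having it, and its comparability with BIOBADASER and BSRBR-RA, whose VTE term lists in Annex 4 carry no position filter.

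**Working it through.** **Step 1: the ARTIS/DANBIO rules side by side.** The last two rows come from the Other medical history table of Annex 4.

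| Row | Setting | Position required | Contributory codes if RA is main |
|---|---|---|---|
| Serious infections | hospitalizations | main | yes |
| Herpes zoster | hospitalizations | main | yes |
| GI perforation | inpatient | main | yes |
| MACE, non-fatal | in- or outpatient | none stated | not needed |
| VTE | in- or outpatient | main | no |
| Infection (history) | inpatient | main | no |
| Diabetes, myocardial infarction (history) | Patient Register | none stated | not needed |

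VTE is broad on setting and strict on position. The cause-of-death route cannot help baseline history, because a patient who starts filgotinib has not died of a pulmonary embolism.

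**Step 2: effect on VTE history.** The protocol states no figure for VTE capture, so there is none to reproduce. Let s be the share of patients with a true past VTE whose code never stands as main diagnosis at any contact. Then observed = true × (1 − s). Both s (5% to 30%) and the true proportions are assumptions.

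- True 5%: 5 × 0.95 = 4.75% and 5 × 0.70 = 3.5%. The shortfall is 0.25 to 1.5 points. Table 11 gives a standard error of 1.3% at 5% and 300 patients.
- True 2%: 2 × 0.95 = 1.9% and 2 × 0.70 = 1.4%. The shortfall is 0.1 to 0.6 points. Table 11 gives 0.8%.

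Only the top of the assumed range is comparable with sampling error at 300 patients. The undercount does not shrink as numbers grow.

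**Step 3: effect on the stop proportion, if the same row is used in follow-up.** A missed VTE leaves both numerator and denominator. The report shows the proportion among captured events (c), while the true value is (1 − s) × c + s × m, with m the proportion among missed events. All values are assumed.

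- c = 80%, m = 80%: the true value is 80%. There is no bias, only fewer events.
- c = 80%, m = 50%: 0.95 × 80 + 0.05 × 50 = 78.5%, and 0.70 × 80 + 0.30 × 50 = 71%.
- c = 80%, m = 95%: 0.95 × 80 + 0.05 × 95 = 80.75%, and 0.70 × 80 + 0.30 × 95 = 84.5%.

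The direction is not fixed. With an assumed 0.5 to 1 VTE per 100 patient-years and 1.5 years each, 300 starters give 300 × 1.5 × 0.005 = 2.25 to 300 × 1.5 × 0.01 = 4.5 events. The loss is then 0.05 × 2.25 = 0.11 to 0.30 × 4.5 = 1.35 events.

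**The case against.** The strongest reply has four parts.

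- **The precedent is narrower than it looks.** The RA exceptions cover hospitalizations or inpatient diagnoses, not outpatient rheumatology visits, and the infection history row has none. This stands. The exceptions support a change only to the inpatient half of the VTE row. For history, the closer precedents are the diabetes and myocardial infarction history rows, with the MACE row as support. These rows are silent on position, so accepting any position is the natural reading of them, not an explicit rule.
- **A contributory code does not erase a main one.** A VTE is missed only if no inpatient or outpatient contact ever lists it as main diagnosis. A reader might infer that every VTE noted at a rheumatology visit is lost, or that the loss falls selectively on events known to the prescriber. The documents support neither. Section 8.4.1 makes some loss plausible: the Swedish Patient Register excludes primary care, and 13% of outpatient visits lack records, with better coverage for most rheumatology care. It does not measure the loss.
- **The link to the stop objective is an inference.** Annex 4 is titled as baseline definitions and Section 8.3.2 does not cite it. The inference is reasonable, since no other VTE code list is given and Section 8.4.4 says DANBIO outcomes come from register linkage, but it is not stated.
- **A blanket widening could do harm.** An old VTE carried as a secondary code at a routine visit could count as an on-treatment VTE without discontinuation and falsely lower the stop proportion. This also stands, and it is why history and follow-up need different rules.

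**Conclusion.** The point holds for baseline history. Applied as written, the Annex 4 VTE row misses past VTEs recorded only in a contributory position, so the proportion with VTE history in ARTIS and DANBIO is biased downward. The amount cannot be derived from the documents. The 5% to 30% relative loss is an assumption and shows scale only.

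For the stop objective the point is weaker. A reader might infer that the proportion is seriously distorted. That needs two things the documents do not give: use of this row in follow-up, and a difference in stopping between captured and missed events. Without such a difference the effect is fewer events. With so few events expected under the assumed rates, the proportion is unstable under any definition. What is plainly missing is a statement of which VTE definition applies in follow-up.

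**What to change.** 1. **Baseline history (Annex 4, for Tables 3 and 7):** accept a listed VTE code in any diagnostic position, dated on or before the index date.
2. **Follow-up VTE:** keep the main-diagnosis rule and add the RA exception for hospitalizations only, as in the infection, zoster and GI perforation rows. Count only VTE codes with no earlier VTE record.
3. **Section 8.3.2:** state that this follow-up definition applies to the VTE discontinuation objective.

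If the strict row is kept instead, Annex 4 should give the reason.

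**Cost:** a few sentences and a changed filter in two registries. A few old or ruled-out VTEs carried as secondary codes will enter the history variable. The no-earlier-record rule also leaves out true recurrences in patients with a VTE history, which the report should say. The lists were built for the companion safety study GS-EU-417-9047, so the VTE definitions of the two studies will differ slightly unless that study is aligned.
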